HIV-1 infected participants who meet all eligibility criteria will be switched from their pre-baseline regimen to an oral regimen (CAB 30 mg + RPV 25 mg once daily) during the **oral lead-in phase**. Participants will return to the clinic, and if laboratory and clinical evaluations continue to support progression into the **injection treatment phase** of the study, will take the last dose of their oral regimen (CAB 30 mg + RPV 25 mg) and receive the first dose of CAB LA (600 mg) + RPV LA (900 mg) injections on the same day (Month 1). The participant will receive the second injections CAB LA (600 mg) + RPV LA (900 mg) one month later (Month 2). All subsequent injections will occur every two months thereafter (Month 4, Month 6, etc) for a total of 7 doses of CAB LA

and RPV LA (Table 7). The total length of the treatment phase is approximately one year.

Table 7 Dosing Regimen

Oral Lead-in to End of Study ⁺		
CAB + RPV Oral Lead-In		
Oral Lead-in (Day 1 to Month 1)	• Take one tablet of CAB 30 mg + RPV 25 mg once daily	
two once daily tablets taken with food		
CAB LA + RPV LA Injections		
Dose 1 (Month 1)	Receive last dose of oral CAB + RPV regimen	
	 Receive CAB LA 600 mg given as 1 X 3 mL IM injection 	
	 Receive RPV LA 900 mg given as 1 X 3 mL IM injection 	
Dose 2 to Dose 7 (Month 2- End of Study ⁺)	 Receive CAB LA 600 mg given as 1 X 3 mL IM injection 	
two 3 mL injections every two months	 Receive RPV LA 900 mg given as 1 X 3 mL IM injection 	
+Until after dose 7 (Month 12) when locally approved and commercially available, the participant no longer derives clinical benefit, the participant meets a protocol-defined reason for discontinuation or until development of CAB LA or RPV LA is terminated		

The dosing window for the second injections will be +0/-7 days from the projected target date (target date is established at Month 1). All subsequent injection windows (starting with Dose 3) will be +7/-7 days from the projected target date. Doses outside of the window *may* be allowed with prior Medical Monitor approval.

Participants will continue CAB LA + RPV LA until:

- After dose 7 and when the study intervention is locally approved and available for the Investigator to prescribe. Note if intervention is not locally approved at dose 7 they will continue into the Extension Phase (see Section 6.8).
- the participant no longer derives clinical benefit
- the participant meets a protocol-defined reason for discontinuation

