4.3.4. LTFU Phase – Following the IM Regimen Only

Any participant who receives *at least one* dose of CAB LA and/or RPV LA and discontinues the CAB LA + RPV LA regimen for any reason before CAB LA + RPV LA marketed product is locally available must enter the LTFU Phase. Participants must remain on suppressive HAART for at least 52 weeks after the last dose of CAB LA and/or RPV LA in order to prevent selective pressure on HIV during the period of declining drug exposures and the potential for selection of resistant mutants.

• Where the CAB LA + RPV LA Marketed Product is Locally Available

Only the participants that discontinue the CAB LA + RPV LA regimen for **safety-related reasons** included in Section 7, must enter the LTFU Phase. Participants must remain on suppressive highly active antiretroviral therapy (HAART) for at least 52 weeks after the last dose of CAB LA and/or RPV LA in order to prevent selective pressure on HIV during the period of declining drug exposures and the potential for selection of resistant mutants.

NOTE: Participants who transition to CAB+RPV LA, marketed product or alternative HAART (except due to safety-related reasons) do not need to enter the LTFU Phase.

Investigators must discuss the choice of the follow-up HAART regimen with the Medical Monitor prior to initiating the new regimen with the participant. HAART therapy should be initiated within one month (- 7 days) after the last dose if interruption is prior to Dose 2 and within 2 months (± 7 days) after the last injection if interruption is following Dose 2, however if withdrawn due to virologic failure, HAART should be initiated as soon as virologic failure is confirmed. Discuss with Medical Monitor. The Long-Term Follow Up period (LTFU) will begin the day of the last CAB LA and/or RPV LA dose and continue for 52 weeks.

Marketed product locally available	Subject WD due to safety- related reasons	LTFU phase required?
No	Yes No	Yes
Yes	Yes	Yes
	No	No, but Safety FU visit required to assess potential safety issues occurred after the last injection see Section 4.5.1.2 Safety Follow-up Visit.

Long term Follow up phase requirement

Participants entering the LTFU phase will not complete a Withdrawal visit but will instead move directly into the LTFU Phase as per the schedule of activities. In addition, for participants who withdraw during the LTFU Phase, the final visit will be considered the study withdrawal visit.

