Participants will be assessed with clinic visits at months 3, 6, 9, and 12 during the LTFU Phase. Female participants of child bearing potential must continue to use adequate contraception methods for the entire year of follow up.

In order to ensure that participants have access to HAART during the LTFU Phase, ViiV Healthcare may supply HAART or reimbursement may be provided as needed during this phase. The LTFU phase may be shortened or terminated at any time during the study for various reasons, e.g., better understanding of risks of development of resistance as CAB and RPV exposures decline, end of study timings, etc.

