6.5.4. Oral Dosing

Any interruption in therapy (ie due to scheduling conflicts, life circumstances, *etc.*) during any oral dosing period that is greater than 3 consecutive days must be noted on the eCRF Bridging Oral/Oral Study Treatment page. Interruptions greater than 7 consecutive days must also be discussed with the Medical Monitor prior to resumption of therapy.

The Medical Monitor must be contacted upon site staff becoming aware of resumption in therapy, if therapy was resumed without prior approval.

Visits for participants in LTFU are expected to occur as projected according to the last injection.

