- m) Withdrawal Visit - Conduct ~4 weeks after the last dose of investigational product (IP) if not entering Long-Term Follow Up and only if the participant has ongoing AEs or lab abnormalities at the last on-study visit. May be conducted by telephone.
- n) Participants receiving one or more injections with CAB LA and/or RPV LA will be assessed with clinic visits at months 3, 6, 9 and 12 during the Long-Term Follow-Up phase. The start of the 52-week follow-up period begins the day of the last CAB LA and/or RPV LA dose.
- o) See protocol Section 8.4.4 for list of tests
- p) Whole blood/PBMC collection samples may be used for virologic analyses. PBMCs will be collected at baseline Day1 and at Withdrawal.
- q) Hepatitis B (HBsAg), Anti-HBc, Anti-HBsAg, Hepatitis C (anti-HCVAb). A (+) anti-HCVAb will be followed by a confirmatory nucleic acid test for HCV RNA. HBV DNA will only be performed for participants with a (+) anti-HBc and (-) HBsAg and (-) anti-HBs (past and/or current evidence).
- r) Administer HIVTSQs in Day 1 before OLI initiation.
- s) At a minimum the study toolkit will be offered at the time pointed noted in the protocol Table 6. However, the toolkit items are intended to be used throughout the study.
- t) Notification of interviews may occur between Day 1 or during the 7 days after Day 1.
- u) Women of childbearing potential should continue to receive counselling on the need to use adequate contraception for the entirety of the Long-Term Follow-Up period.
- v) Investigators must discuss choice of HAART regimen and timing of initiation with the Medical Monitor before initiating.

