Table 4 Assessment Windows for Study Visit Length Data (Intervention and Extension Phase)

Target (Study Day)	Analysis Window		Analysis Timepoint
	Beginning Timepoint	Ending Timepoint	
Study Day of Actual M1 Injection	Study Day of Actual M1 Injection		Month 1
Study Day of Actual M2 Injection	Study Day of Actual M2 Injection		Month 2
Study Day of Actual M6 Injection	Study Day of Actual M6 Injection		Month 6
Study Day of Actual M8 Injection	Study Day of Actual M8 Injection		Month 8
Study Day of Actual Mx Injection	Study Day of Actual Mx Injection		Month x For x=17, 20, etc.
	If none of the above, then Analysis Timepoint = Other		

Table 5 Assessment Windows for Summaries of Long-Term Follow-up Phase Data from Subjects who Received at Least One Injection of CAB+RPV and Permanently Discontinued from the Study

Day of Assessment	Assessment Window	Target LTFU Study Day of Window
$1 \leq \text{LTFU Study Day} \leq 135$	LTFU Month 3	90
$136 \leq \text{LTFU Study Day} \leq 225$	LTFU Month 6	180
$226 \leq \text{LTFU Study Day} \leq 315$	LTFU Month 9	270
$316 \leq \text{LTFU Study Day} \leq 405$	LTFU Month 12	360
$(30*m-44) \leq \text{LTFU Study Day} \leq (30*m+45)$	LTFU Month m M = 15, 18, 21	30*m

- LTFU Study Day is defined in 13.5.1

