
Study Day
 
 • The Study Day of an event (e.g., lab assessment, vital sign, ECG, start date of AE or HIV associated condition) will be derived as the number of days between the date of the event and the Intervention Phase treatment start date as follows: 
 ○ If date of event \geq start date of study treatment, then 
 ▪ Study Day = Date of Event - Intervention Phase Treatment Start Date +1 ○ If date of event $<$ start date of study treatment, then 
 ▪ Study Day = Date of Event - Intervention Phase Treatment Start Date • Note that the start date of intervention phase study treatment is on Study Day 1 and the day before this is Study Day -1; i.e., there is no Study Day 0.

Long Term Follow-up Study Day

 Participants are considered to have entered LTFU if they have a post-treatment, non-bridging ART medication start date or a LTFU visit entered in the CRF. The Long-Term Follow Up (LTFU) Study Day of an event (e.g., lab assessment, start date of AE or HIV associated condition) will be derived as the number of days between the date of the event and the end of IP treatment [i.e. min(LTFU ART Start Date, max>Last IM Injection Date, Last Oral Bridging End Date)] as follows: 
 If the date of event falls in Long-term Follow up phase, then 
 LTFU Study Day = Date of event - min(LTFU ART Start Date, max>Last IM Injection Date, Last Oral Bridging End Date) + 1
Study Treatment

 Refers to CAB+RPV oral lead-in, CAB + RPV oral bridging, SOC bridging, CAB LA + RPV LA
Change from Baseline

 Post-Dose Visit Value – Baseline 
 Unless otherwise specified, the baseline definitions specified in Section 5.2 will be used for derivations for endpoints / parameters.

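### SAP 13.5.1 starts the LTFU clock at the end of oral bridging instead of the last injection, so participants who stopped after bridging have their Month 6, 9 and 12 follow-up visits slotted too early

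*SAP*

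**What the plan says.** **Start of follow-up.** Protocol 4.3.4 states: "The Long-Term Follow Up period (LTFU) will begin the day of the last CAB LA and/or RPV LA dose and continue for 52 weeks". Protocol 7.1 and footnote n of the protocol's Table 1 use the same origin. The SAP repeats the footnote in 13.1.1: "The start of the 52-week follow-up period begins the day of the last CAB LA and/or RPV LA dose".

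**Visit schedule.** Protocol 4.3.4: "Participants will be assessed with clinic visits at months 3, 6, 9, and 12 during the LTFU Phase". Protocol 6.5.4 adds: "Visits for participants in LTFU are expected to occur as projected according to the last injection".

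**Study day in the SAP.** The derivation in SAP 13.5.1 opens with "LTFU Study Day = Date of event - min(LTFU ART Start Date" and in full reads: "LTFU Study Day = Date of event - min(LTFU ART Start Date, max>Last IM Injection Date, Last Oral Bridging End Date) + 1". The bracket after max is garbled in the text, but the meaning is clear: the origin is the earlier of LTFU ART start and the later of last injection and last oral bridging end. The SAP describes this origin as the end of IP treatment.

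**Windows.** SAP Table 5 (13.2.1) slots LTFU Study Day as Month 3 = 1 to 135, Month 6 = 136 to 225, Month 9 = 226 to 315 and Month 12 = 316 to 405, with targets 90, 180, 270 and 360. Under SAP 13.5.1, when two values share a window, the one closer to the target is summarised.

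**The concern.** The visit schedule and the window targets share one origin, the last injection. The study day that is slotted into those windows uses another. For a participant who went from injections straight to follow-up ART, the minimum returns the last injection and nothing is lost. For a participant who bridged orally after the last injection and then stopped, the origin moves to the end of the bridge (or to LTFU ART start, if that is earlier) while the visits stay where they were.

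On-schedule visits then carry the label of an earlier visit. A by-visit LTFU summary would mix participants at different times since their last long-acting dose, in a phase that protocol 4.3.4 ties to the period of declining drug exposure.

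**Working it through.** **Formula.** Let d be the days from last injection to visit, and s the days from last injection to the SAP origin. Then LTFU Study Day = d − s + 1.

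**Table 5 reproduced.** The rule 30m − 44 to 30m + 45 gives 136–225, 226–315 and 316–405 for m = 6, 9 and 12. For m = 3 it gives 46–135, which the SAP extends down to day 1. These are the SAP's bounds.

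**Slotting, with visits at d = 90, 180, 270, 360.** Each cell shows LTFU Study Day → window.

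| s | Month 3 visit | Month 6 visit | Month 9 visit | Month 12 visit |
|---|---|---|---|---|
| 0 | 91 → M3 | 181 → M6 | 271 → M9 | 361 → M12 |
| 45 | 46 → M3 | 136 → M6 | 226 → M9 | 316 → M12 |
| 46 | 45 → M3 | 135 → M3 | 225 → M6 | 315 → M9 |
| 61 | 30 → M3 | 120 → M3 | 210 → M6 | 300 → M9 |
| 90 | not LTFU | 91 → M3 | 181 → M6 | 271 → M9 |
| 120 | not LTFU | 61 → M3 | 151 → M6 | 241 → M9 |
| 135 | not LTFU | 46 → M3 | 136 → M6 | 226 → M9 |
| 136 | not LTFU | 45 → M3 | 135 → M3 | 225 → M6 |
| 150 | not LTFU | 31 → M3 | 121 → M3 | 211 → M6 |

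The cells marked not LTFU follow from SAP Table 8. A laboratory value enters the LTFU phase only if it is dated after LTFU ART start, and the origin is never later than that date. With a recorded ART start, every slotted laboratory value therefore has LTFU Study Day 2 or more. A Month 3 visit made while still bridging belongs to the Intervention or Extension phase.

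**Thresholds.** No visit moves for s ≤ 45. One window is lost from s = 46 (for Month 12: 360 − 46 + 1 = 315). Two windows are lost by Months 9 and 12 from s = 136 (270 − 136 + 1 = 135; 360 − 136 + 1 = 225). With calendar visit days of 91, 183, 274 and 365, the one-window threshold is 49 to 51 and the two-window threshold 140 to 141.

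**Values of s that can occur.** Protocol 6.5.1.2 and 10.14.3 place the start of bridging inside the dosing window of the missed injection. From Dose 3, "All subsequent injection windows (starting with Dose 3) will be +7/-7 days from the projected target date". On two-monthly dosing a bridge thus starts at about day 60 − 7 = 53 to 61 + 7 = 68, already past the one-window threshold. A bridge from day 60 lasting 30, 60 or 90 days gives s = 90, 120 or 150. Protocol 6.5.1.1 limits oral CAB + RPV bridging to 3 months; 6.5.1.2 states no limit for standard-of-care bridging. A two-window shift needs a bridge of at least about 136 − 68 = 68 to 141 − 53 = 88 days. After Dose 1 the next injection is due at one month, so a short bridge ending by about day 45 moves nothing.

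**Displacement.** At s = 61 the Month 3 and Month 6 visits (LTFU days 30 and 120) share the Month 3 window. Their distances from day 90 are 60 and 30, so the Month 6 value is summarised as Month 3 and the true Month 3 value appears only in listings. At s = 150 the Month 6 and Month 9 visits (days 31 and 121) share it, at distances 59 and 31, so a value taken 270 days after the last injection is reported as Month 3.

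**The case against.** The strongest defence is that the origin is deliberate: the SAP names it as the end of IP treatment. A participant on daily oral CAB + RPV is still receiving both drugs, so counting from the end of that bridge is an arguable convention. This stands in part for CAB + RPV bridging. It does not extend to standard-of-care bridging, which SAP 13.5.1 counts as study treatment but which is not IP under protocol 6.1. For neither type does it explain why Table 5 kept windows that fit a schedule counted from the injection, or why footnote n states the other origin.

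The second defence is reach, and it largely stands. Bridging with CAB + RPV is reserved for exceptional circumstances (protocol 6.5.1.1). It must also be the last treatment before stopping, and once marketed product is locally available only safety-related discontinuations must enter LTFU. The documents give no count, and it could be zero.

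A reader might infer more than the documents support:

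- *Everyone who bridged has an empty Month 12 window.* Participants who resumed injections have a later last-injection date, the maximum returns it, and they are unaffected.
- *Every visit moves by one or two windows.* Month 3 cannot move earlier, and Month 6 moves by at most one.
- *Resistance or drug-tail findings are distorted.* PK data are listed by nominal visit (SAP 13.2.2). The resistance tables (2.9 to 2.11) use the Safety population and are organised by virologic failure status. The LTFU adverse event tables (3.14, 3.21, 3.29, 3.34) are by system organ class.

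**Conclusion.** The derivation is wrong as written, and of low severity. It contradicts protocol 4.3.4, 6.5.4 and 7.1 and the SAP's own footnote n, and it does not match the windows it feeds. It matters only for participants whose last treatment was oral bridging.

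For them, an origin about 46 to 135 days after the last injection shifts Months 6, 9 and 12 one window early; from about 136 days, Months 9 and 12 shift two and Month 6 one. With an origin beyond about 45 to 50 days, no on-schedule visit reaches the Month 12 window.

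The listed by-visit displays exposed are Tables 3.41 and 3.44 (LTFU chemistry and hematology changes from baseline). SAP 7.1.2 also promises LTFU HIV-1 RNA summaries, although Tables 2.1 to 2.16 contain no LTFU-population display; any by-visit version would be exposed too. The primary endpoint comes from staff questionnaires and interviews and is untouched.

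The result assumes that visits occur on schedule and that a bridge starts in the missed-dose window. The choice between 30-day and calendar months moves the thresholds by no more than about five days.

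**What to change.** For slotting into Table 5, define LTFU Study Day = date of event − date of last CAB LA and/or RPV LA injection + 1, for all participants. This is the s = 0 row of the table: on-schedule visits return to Months 3, 6, 9 and 12, and nothing changes for participants whose last treatment was an injection. A participant still bridging at Month 3 would correctly have no LTFU Month 3 value.

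Leave phase assignment (SAP 13.3.1) and on-treatment status (13.3.2) as they are; neither uses LTFU Study Day. If the sponsor prefers the end-of-treatment origin, the SAP should justify it, reconcile it with footnote n and re-derive Table 5.

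The cost is one formula in the SAP and its program, plus a rerun of Tables 3.41 and 3.44 if already produced. Data collection, the visit schedule and clinical management are unaffected.

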13.5.2. Study Population

Demographics
Age

 Age, in whole years, will be calculated with respect to the subject’s Screening visit. GSK standard IDSL algorithms will be used for calculating age where birth date will be imputed as follows: 
 Any subject with a missing date and month will have this imputed as ‘30th June’. Birth date will be presented in listings as ‘YYYY’. Completely missing dates of birth will remain as missing, with no imputation applied. Consequently, the age of the subject will not be calculated and will remain missing.
Body Mass Index

 Calculated as Weight (kg)/Height (m)²
Hepatitis Status

 Hepatitis C status will be determined using antibody and/or hepatitis C virus (HCV) RNA assessments performed during screening or during the conduct of the study. If both antibody and virus RNA assessments are available, then the latter will take precedence and positive/negative status will be based on whether HCV RNA is detectable (i.e., ≥ limit of quantification) or not. A participant will be considered positive for hepatitis B virus (HBV) if they have a positive surface antigen or detectable HBV DNA result. “HBV DNA DETECTED” in the lab comment takes precedence over HBV DNA test result for positive hepatitis B status; for example, if a participant has HBV DNA test result below level of detection and the lab comment shows that HBV DNA detected, this participant will be considered positive for hepatitis B. If HBV DNA result is available, it will be used to qualify hepatitis B status as positive or negative (positive if ≥ limit of quantification); otherwise Hepatitis B status will be determined using the surface antigen result. Hepatitis status at entry will be based on the assessments prior to/on the start of the study treatment.
Adherence to CAB/RPV Injection Schedule

 Timeliness of Injections relative to Date of Projected Dosing Visits are assessed by using "actual injection visit date - projected visit date from first injection". The injections of interest in adherence

Demographics

analysis are those after first injection at Month 1. (. Each injection visit is counted only once. Individual CAB and RPV injections administered at the same visit are not counted twice. "Extra" unscheduled injections are excluded from all derivations. For example, if during a scheduled visit a participant receives 1 ml of injection instead of 2 ml due to a dosing error, but this participant returns one week later for the remaining 1 ml injection, then the additional visit is excluded. If a participant receives an extra injection at an unscheduled visit by mistake, this visit will also be excluded.

- The categories of Timeliness of Injections relative to Date of Projected Dosing Visits are listed below:
 - < -14 days
 - -14 to - 8 days
 - -7 to 1
 - 0
 - 1 to 7 days
 - 8 to 14 days
 - >14 days
 - Missed Injection without Oral Bridging (COVID-19 related)
 - Missed Injection without Oral Bridging (Non COVID-19 related)
 - Missed Injection with Oral Bridging (COVID-19 related)
 - Missed Injection with Oral Bridging (non COVID-19 related)
 - Missed Injection with subsequent SOC ART Initiation
- The following categories surrounding out of window (OOW) visits will also be calculated separately for participants at each visit.
 - Oral Bridging without a Missed Injection
 - OOW Injection with Oral Bridging (non-Covid-19 related)
 - OOW Injection with Oral Bridging (Covid-19 related)
 - OOW Injection without Oral Bridging (Covid-19 related)
- Injection visits are expected bi-monthly after an initial Month 1 Q4W injection from Month 2 until the nominal month of a participant's last injection visit during the phase(s) of interest. For example:
 - If a participant discontinues study treatment with last injection visit occurring at nominal visit Month 6, then injection visits are expected at Month 1, Month 2, Month 4, and Month 6.
- Expected injection visits will include all treatment visits (not LTFU) where an assessment was recorded regardless of whether the injection took place, including visits where treatment was discontinued.
- Missed injections with subsequent LTFU SOC ART Initiation are not counted in 'Missed Injection without Oral Bridging' categories. Missed injections will be slotted to this category if LTFU SOC ART is initiated within 30 days of the missed injection.
- Out of Window injections are determined based on criteria listed in protocol Section 4.3.3.
- Covid-19 relatedness is determined as follows:
 - As labelled in concomitant medication or exposure as Oral Bridging due to Covid-19
 - As indicated by Covid-19 protocol deviations that occur on the impacted visit date

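### SAP 13.5.2 defines expected injection visits by two unranked rules, and neither counts a participant who misses an injection visit unassessed and never returns

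*SAP*

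**What the plan says.** The fidelity endpoint is the percentage of injections given within the window around the target date (SAP 2.2; protocol 9.4.2). SAP 13.5.2, under adherence to the injection schedule, builds its denominator.

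- **Last-injection rule.** Visits are expected from Month 2 up to the month of the "last injection visit during the phase(s) of interest". In the worked example, a participant who discontinues after a Month 6 injection has visits expected at Months 1, 2, 4 and 6.
- **Recorded-assessment rule.** The next main bullet reads: "Expected injection visits will include all treatment visits (not LTFU) where an assessment was recorded regardless of whether the injection took place". It explicitly covers the visit at which treatment is discontinued.
- **Separate category.** An injection missed shortly before long-term follow-up (LTFU) therapy has its own row: "Missed injections will be slotted to this category if LTFU SOC ART is initiated within 30 days of the missed injection". SAP Section 1 gives this separation as a reason for Amendment 1.
- **Scope.** The injections of interest in the adherence "analysis are those after first injection at Month 1".

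No precedence between the two rules is stated. Shells SAF_T1 and SAF_T2 (SAP 13.13) show the number of expected visits in columns from Month 2 to Month 12, with four missed-injection rows. The row for a miss followed by standard-of-care ART is not among them.

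**The concern.** A denominator that ends at the last injection received depends on the outcome being measured: the final expected visit is always one at which the injection was given. A miss that leads straight into dropout then disappears instead of counting against fidelity. Under the protocol, loss to follow-up means repeatedly failing to attend (7.3), so for these participants a missed visit comes before the withdrawal. Protocol 2.2.2 names missed injections among the worries that motivate the study.

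Fidelity is one of the five implementation outcomes in protocol 4.2.2. The adherence tables are produced by country and site, and by implementation strategy as a subgroup (SAP 13.12.7, Tables 3.3 to 3.6). A denominator that shrinks with dropout flatters the sites, or the arm, where more participants leave. Separately, two programmers following different bullets would report different numbers from the same data.

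**Working it through.** **1. The SAP's own example.** The injection schedule is Months 1, 2, 4, 6, 8, 10 and 12 (protocol 1.3). With the last injection at Month 6, counting every scheduled visit up to it gives {1, 2, 4, 6} = 4, as the SAP states ("injection visits are expected at Month 1, Month 2, Month 4, and Month 6"). The SAP's start at Month 2, and its restriction to injections after the first, give {2, 4, 6} = 3. The steps below exclude Month 1.

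**2. The rules applied to single participants.** The numerator is injections received.

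| Participant | Last-injection rule | Recorded-assessment rule |
|---|---|---|
| Injected to Month 6; attends Month 8, assessed, not injected, discontinues | 3/3 = 100% | 3/4 = 75% |
| Injected to Month 6; absent at Month 8, no assessment, never returns | 3/3 = 100% | 3/3 = 100% |

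In the second row the Month 8 miss enters neither denominator. If Month 8 were expected by its target date, the result would be 3/4 = 75%. By contrast, a participant who misses Month 4 and is injected at Month 6 has {2, 4, 6} expected under the last-injection rule and scores 2/3, so that miss is counted.

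**3. The standard-of-care ART category.** LTFU ART is post-treatment and non-bridging (SAP 13.3.1), so an injection missed just before it falls after the last injection received. The last-injection rule has by then stopped expecting visits. Applied alone, it leaves this category empty.

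**4. Size.** Inputs from the documents: 450 evaluable patients, 474 enrolled and 18 sites (SAP 2.4.1), and six scheduled injections after Month 1. Assumed: the share of participants with an uncounted miss, and one such miss each.

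Simple form: 450 × 6 = 2,700 expected; 5% × 450 = 22.5 misses; 22.5 / 2,700 = 0.83 points.

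Refined form, with each dropout last injected at Month 6 (3 expected visits instead of 6) and a share p of the counted visits in window: reported = p; with the misses restored = p × D / (D + d), where D is the last-injection denominator and d the number of dropouts.

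| Dropouts d | D | D + d | p = 90% becomes | p = 95% becomes |
|---|---|---|---|---|
| 22 of 450 | 428×6 + 22×3 = 2,634 | 2,656 | 89.25% (−0.75) | 94.21% (−0.79) |
| 24 of 474 | 450×6 + 24×3 = 2,772 | 2,796 | 89.23% (−0.77) | 94.18% (−0.82) |
| 45 of 450 | 405×6 + 45×3 = 2,565 | 2,610 | 88.45% (−1.55) | 93.36% (−1.64) |

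At an average site, 450 / 18 = 25 patients give 25 × 6 = 150 expected visits. Three such dropouts move the simple figure by 3 / 150 = 2.0 points.

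**The case against.** The two bullets can be read together: the first sets the schedule and its end, and the second adds attended visits without an injection. On that reading they do not conflict and the standard-of-care ART row can be filled. This is a fair reading, and arguably the more natural one, since the SAP would hardly define a row that must stay empty. But the SAP does not state it and the example stops at the last injection, so the missing precedence stands as a defect. The additive reading also does nothing for a no-show with no assessment.

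A reader might infer that no missed injection before dropout is ever counted. The documents do not support that. A miss followed by a later injection is counted, and one at an assessed visit is counted under the second rule. Withdrawal visits are slotted to assessment windows (SAP 13.6.1), although participants entering LTFU skip that visit (protocol 4.3.4).

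A reader might also infer that the Month 1 dose, on time by definition because it sets the target date, inflates the results; counting it would turn 85% into (6 × 0.85 + 1) / 7 = 87.1%. It appears only in the example. The scope sentence, the start at Month 2 and both shells exclude it.

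Keeping participants who start LTFU ART apart from other missed injections was a deliberate amendment and is not an error.

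Finally, the endpoint could be read as conditional on an injection being given, and withdrawals are reported elsewhere (Tables 1.2 to 1.4, Listings 1 and 2). Those displays do show dropout. The adherence shells, however, use expected visits as their base and carry missed-injection rows, so that base needs a definition that does not depend on the outcome.

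**Conclusion.** The point holds in limited form. The two rules lack a stated precedence and can give 100% or 75% for the same participant. If the last-injection rule is used alone, injections missed after the last one received are never expected, and the standard-of-care ART row is empty. Under both rules, an unassessed miss followed by permanent absence is lost, which biases fidelity upwards where such dropout occurs.

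The trial-level effect is modest: about 0.8 points if 5% of 450 participants each have one uncounted miss. The documents give 5% only as the non-evaluable share, not as a rate of such misses, and participants can stop for other reasons without missing a dose. The 10% row has no source in the documents and shows sensitivity only. The endpoint is descriptive, so no hypothesis test is affected; the practical risk is to comparisons between sites and between arms.

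**What to change.** Replace the two bullets in SAP 13.5.2 with one rule.

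- A nominal injection visit from Month 2 onwards is expected if its target date plus the allowed window falls on or before the earliest of: phase end; transition to commercial product; LTFU ART start; and the recorded date of the decision to discontinue treatment or of being declared withdrawn or lost to follow-up. It is expected whether or not an assessment was recorded. The last dose date must not serve as the discontinuation date, since that would bring back the present problem for no-shows.
- In addition, keep every attended scheduled treatment visit, injected or not, including the discontinuation visit, as the second rule already provides.
- Keep a due injection that was not given and was followed by LTFU ART within 30 days in its own row, apart from the other missed-injection rows, as Amendment 1 intended. Add that row to SAF_T1 and SAF_T2.
- As an editorial correction, delete Month 1 from the worked example.

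The cost is SAP wording, minor reprogramming and a slightly less favourable percentage. No new data collection is needed.
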